2.1 Assessment and Informed Consent/Assent

A subject is considered for the study after undergoing an eye examination by an investigator (as part of standard care) that identifies amblyopia meeting the eligibility criteria. As noted in subsequent sections, if applicable, refractive error must be corrected with glasses (as per standard care) before a subject can be enrolled into the trial.

For subjects who appear eligible for the study following a “standard-care” examination, the study will be discussed with the child’s parent(s) or guardian. Parents or guardians who express an interest in the study will be given a copy of the consent form. Written informed consent will be obtained from the parent or guardian and assent from appropriately-aged subjects prior to performing any study-specific procedures that are not part of the subject’s routine care. Sites will keep a log of the number of subjects who were eligible but not enrolled.

2.2 Eligibility and Exclusion Criteria

2.2.1 Eligibility

The following criteria must be met for the subject to be enrolled in the study:

1. Age 8 to < 18 years
2. Amblyopia associated with strabismus (comitant or incomitant), anisometropia, or both
 - Criteria for strabismus: At least one of the following criteria must be met:
 - Heterotropia at distance and/or near fixation on examination (with or without spectacles)
 - History of strabismus surgery
 - Documented history of strabismus which is no longer present (which in the judgment of the investigator could have caused amblyopia)
 - Criteria for anisometropia: At least one of the following criteria must be met:
 - ≥ 0.50 D difference between eyes in spherical equivalent
 - ≥ 1.50 D difference between eyes in astigmatism in any meridian
3. Visual acuity, measured in each eye (amblyopic eye without cycloplegia) within 7 days prior to enrollment using the E-ETDRS protocol on a study certified visual acuity tester as follows:
 - Visual acuity in the amblyopic eye 18 to 67 letters inclusive (20/50 to 20/400)
 - Visual acuity in the sound eye ≥ 78 letters (20/25 or better)
 - No improvement in best-corrected amblyopic eye visual acuity between two consecutive visits at least 4 weeks apart using the same testing method and optimal spectacle correction (if needed), with no improvement of more than 4 letters or one logMAR line
4. Current amblyopia treatment (other than spectacles)

- 546 • At least two hours of occlusion per day prescribed for the sound eye and performed
- 547 during the same period of time during which the two measurements of visual acuity at
- 548 least 4 weeks apart were obtained (and visual acuity was not improved).
- 549 • Treatment with atropine during this period is not allowed.
- 550 • Any treatment prior to the current patching episode with stable acuity is acceptable.
- 551 5. Spectacle correction (if applicable) for measurement of enrollment visual acuity must meet
- 552 the following criteria and be based on a cycloplegic refraction that is no more than 6
- 553 months old:
- 554 a. Requirements for spectacle correction:
- 555 • Spherical equivalent must be within 0.50 D of fully correcting the anisometropia.
- 556 • Hypermetropia must not be undercorrected by more than 1.50 D spherical
- 557 equivalent, and reduction in plus sphere from the most recent cycloplegic
- 558 refraction must be symmetric in the two eyes.
- 559 • Cylinder power in both eyes must be within 0.50 D of fully correcting the
- 560 astigmatism.
- 561 • Cylinder axis in both eyes is within 6 degrees of the axis in the spectacles when
- 562 cylinder power is ≥ 1.00 D.
- 563 • Myopia of amblyopic eye greater than 0.50 D by spherical equivalent must be
- 564 corrected, and the glasses must not undercorrect the myopia by more than 0.25 D
- 565 or overcorrect it by more than 0.50 D.
- 566 b. Spectacles meeting above criteria must be worn either:
- 567 1) for 16 weeks immediately prior to enrollment, or
- 568 2) until visual acuity in amblyopic eye is stable (defined as two consecutive visual
- 569 acuity measurements by the same testing method at least 4 weeks apart with no
- 570 improvement of more than 4 letters or one logMAR line)
- 571 • An acuity measurement done any of the following ways may be considered the
- 572 first of two consecutive measurements: 1) in current glasses, 2) in trial frames
- 573 with full correction of hypermetropia with cycloplegia, or 3) by having the subject
- 574 return in new glasses for first measurement. *Note: since this determination is a*
- 575 *pre-study procedure, the method of measuring visual acuity is not mandated.*
- 576 6. Ocular examination within 6 months prior to enrollment
- 577 7. Parent available for at least 4 months of follow-up, has home phone (or access to phone),
- 578 and willing to be contacted by clinical site staff and Jaeb Center staff
- 579 8. In the investigator's judgment, the subject is likely to comply with prescribed treatment
- 580 (e.g., no history of poor compliance with patching treatment).

581
582 **2.2.2 Exclusions**

- 583 1. Myopia more than -6.00 D (spherical equivalent) in either eye.

- 584 2. Current vision therapy or orthoptics
585 3. Ocular cause for reduced visual acuity
586 • nystagmus per se does not exclude the subject if the above visual acuity criteria are met
587 4. Prior intraocular or refractive surgery
588 5. History of narrow-angle glaucoma
589 6. Strabismus surgery planned within 16 weeks
590 7. Known allergy to levodopa-carbidopa
591 8. History of dystonic reactions
592 9. Current requirement to take oral iron supplements including multivitamins containing iron
593 during treatment with levodopa-carbidopa
594 10. Current use of antihypertensive, anti-depressant medications, phenothiazines,
595 butyrophenones, risperidone and isoniazid, non-specific monoamine oxidase inhibitors
596 11. Current use of medication for the treatment of attention deficit hyperactivity disorder
597 12. Known gastrointestinal or liver disease
598 13. History of melanoma
599 14. Known psychological problems
600 15. Known skin reactions to patch or bandage adhesives
601 16. Prior levodopa treatment
602 17. Current treatment with topical atropine
603 18. Females who are pregnant, lactating, or intending to become pregnant within the next 16
604 weeks.
605 • A negative urine pregnancy test will be required for all females who have experienced
606 menarche.
607 • Requirements regarding the establishment of pregnancy status and monitoring for
608 pregnancy over the course of the study as defined by each individual Institutional Review
609 Board may supersede these criteria.

610

611 **2.3 Examination Procedures**

612 **2.3.1 Historical Information**

613 Historical information elicited will include the following: date of birth, gender, ethnicity, prior
614 amblyopia therapy (e.g., glasses, patching, pharmacologic, Bangerter filters, combined therapies,
615 near activities with treatment), corrected visual acuity before amblyopia treatment started (if
616 available), current amblyopia therapy, current spectacle correction, and history of the following:
617 allergy to adhesive skin patches, allergy to levodopa-carbidopa, narrow-angle glaucoma,
618 dystonic reactions, gastrointestinal or liver disease, melanoma, psychological problems.

619

620 **2.3.2 Clinical Testing**

621 Examination procedures include:

- 622
623 1. Measurement of body weight.
- 624 2. Measurement of visual acuity in each eye (right eye first) by the E-ETDRS testing protocol
625 on a study approved visual acuity tester.
- 626 • Testing of the amblyopic eye must be done without cycloplegia (with spectacles, if worn)
627 no more than 7 days prior to enrollment.
- 628 • Subjects currently wearing spectacles must have enrollment acuity measured while
629 wearing spectacles; trial frames or phoropter cannot be used.
- 630 3. Ocular motility examination
- 631 • Measurement of alignment by Simultaneous Prism and Cover Test (SPCT) in primary
632 position at distance and near
- 633 • If performed within prior 7 days, alignment measurements do not need to be repeated at
634 time of enrollment
- 635 4. Stereoacuity testing: Titmus fly, Randot Preschool test
- 636 5. Complete ocular examination, including dilated fundus examination, to rule out a cause for
637 reduced visual acuity other than amblyopia.
- 638 • If performed within prior 6 months, the ocular examination does not need to be repeated
639 at time of enrollment
- 640 6. Cycloplegic refraction using cyclopentolate 1% as per investigator's usual routine
- 641 • If performed within prior 6 months, the cycloplegic refraction does not need to be
642 repeated at time of enrollment

643
644 **2.3.3 Symptom Survey**

645 Each subject (or parent if subject is unable to complete) will complete a symptom survey to
646 identify any symptoms they may be experiencing before beginning treatment. The questionnaire
647 will be repeated at each follow-up visit.

648
649 **2.3.4 Randomization**

650
651 **Randomization of Eligible Patients**

- 652 1. Once a subject is randomized, that subject will be included in the analysis regardless of
653 whether the assigned treatment is received or not. Thus, the investigator must not
654 randomize a subject until he/she is convinced that the parent/guardian will accept and
655 comply with either of the treatment regimens.
- 656 2. A subject should not be randomized until both the investigator and parent are ready to start
657 protocol-mandated treatment.
- 658 3. The Jaeb Center will construct a Master Randomization List using a permuted block design
659 stratified by visual acuity in the amblyopic eye as moderate 20/50 to 20/80 (53 to 67
660 letters) versus severe 20/100 to 20/400 (18 to 52 letters), which will specify treatment
661 group assignments. A subject is officially enrolled when the website randomization

662 process is completed. Both the subject and the site will be masked to treatment group
663 assignment.

664

665 **Delay in Randomization**

- 666 1. Visual acuity testing and the ocular motility examination must be performed no more than
667 7 days prior to randomization. If randomization is delayed beyond 7 days, then these tests
668 must be repeated to confirm eligibility and establish the baseline measures for the study.
669 2. No other parts of the examination (including the refraction) need to be repeated if they
670 were performed within 6 months prior to randomization.
671

Chapter 3: Treatment

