7.1 Sample Size and Analysis

This pilot study is being conducted as a prelude to conducting a randomized trial. The purpose of the pilot study is to evaluate two different dosages of levodopa and provide prospective data on the tolerability of levodopa as a treatment for amblyopia and to provide limited data on its safety. In addition, this study will address whether oral levodopa with patching improves the visual acuity of subjects with residual amblyopia.

Approximately 30 subjects will be enrolled by participating sites (each site will enroll no more than 5 subjects). Recruitment will continue until a fixed date. If a subject signs informed consent they will be allowed to enroll into the study. Subjects will be randomized to one of two levodopa dosage subgroups (0.51 mg/kg versus 0.76 mg/kg) in a 1 to 1 ratio.

Tabulations and computations will be done within the two dosage subgroups and will include the following:

- Proportion of subjects completing the treatment course and proportion discontinuing treatment due to side effects, with 95% confidence intervals.
- Listing of all reported adverse events.
- For each visit, proportion of subjects with improvement in amblyopic eye visual acuity of 10 or more letters, with 95% confidence interval; to be used to estimate magnitude of treatment effect for a subsequent RCT. Subjects who drop from the study will be considered to have not improved.
- The number of subjects per site enrolled will be calculated to estimate recruitment potential for a subsequent randomized trial.
- The proportion of eligible subjects enrolled will be calculated to estimate recruitment potential and the willingness of parents and subjects to participate.

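### The entry stability rule limits improvement but not decline, and the enrolment reading also appears to be the baseline, so the mean acuity gain is inflated and the 10-letter responder rate modestly inflated, with no untreated arm to cancel it

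*Protocol*

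**What the plan says.** Protocol 2.2.1 item 3 sets the acuity criteria for an E-ETDRS test within 7 days before enrolment. One is the entry window: "Visual acuity in the amblyopic eye 18 to 67 letters inclusive (20/50 to 20/400". Another, under the same item, is stability between two consecutive visits at least four weeks apart, "with no improvement of more than 4 letters or one logMAR line". Item 5b uses the same limit for spectacle wear, which must last 16 weeks or "until visual acuity in amblyopic eye is stable (defined as two consecutive visual" acuity measurements that show no "improvement of more than 4 letters or one logMAR line". Neither item limits a fall.

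Section 2.3.4 (Delay in Randomization) says that if more than 7 days pass, the acuity and motility tests "must be repeated to confirm eligibility and establish the baseline measures for the study". One reading thus does both jobs, and no separate baseline after qualification is planned.

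Section 7.1 computes, within each dose group, the "proportion of subjects with improvement in amblyopic eye visual acuity of 10 or more letters", which is "to be used to estimate magnitude of treatment effect for a subsequent RCT". Table 7-4 turns the count out of 15 into a decision: 1 is Don't Proceed, 2 to 4 Uncertain, 5 or more Proceed. Both groups receive levodopa plus patching (1.1), and 7.2 plans no formal comparison between them.

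**The concern.** A rule that rejects children whose second reading rose, but keeps those whose second reading fell, selects second readings that are low by chance. The 67-letter ceiling on the same reading selects in the same direction, more weakly. If that reading is the baseline, later readings drift up on average with no treatment effect. A child who reads 60, then 50 at enrolment, then 60 at Visit 2 counts as improved, having only regained what was lost before the drug began.

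With no untreated arm, nothing subtracts this drift. The responder proportion feeds Table 7-4, where one child separates 4 of 15 from 5 of 15, and it informs the effect size for the next trial. Section 1.1 adds that an absence of acuity improvement might be enough to abandon that trial, so the ability to recognise no effect matters.

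**Working it through.** **Table 7-4.** The printed limits mostly follow p ± 1.96·√(p(1−p)/15). For 5/15: 0.333 ± 0.239, or 9.5% to 57.2% (printed 10% to 57%). For 1/15 the upper limit is 19.3% (printed 19%). For 4/15 it is 49.0% (printed 50%). The cut-offs reproduce: 2 or more of 15 escapes Don't Proceed, and 5 or more is Proceed.

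**Inputs.** From the protocol: window 18 to 67 letters; second reading minus first no more than +4; responder if outcome minus baseline is at least 10; about 15 per dose (30 subjects, 1:1). Assumed, because the protocol does not give them: true acuity normal with mean 50 and SD 15 letters; independent normal error with SD 3, 4 or 5 letters per reading, rounded to whole letters.

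**Method.** Simulate reading 1, reading 2 (enrolment) and the Visit 2 reading with zero true change, and keep eligible children. Compare four versions: the rule as written; the same rule with a fresh baseline reading after qualification; a two-sided limit of 4 letters; and the rule as written with the mean of the two readings as baseline. Then P(≥2 of 15) = 1 − (1−p)^15 − 15p(1−p)^14. For p = 0.061 this is 1 − 0.389 − 0.379 = 0.23.

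| No true change, error SD 3 / 4 / 5 | Mean gain (letters) | Responders (%) | P(≥2 of 15) (%) |
|---|---|---|---|
| As written | 0.65 / 1.2 / 1.7 | 1.5 / 6.1 / 12.1 | 2 / 23 / 55 |
| Fresh baseline | 0 / 0 / 0 | 1.3 / 4.7 / 9.0 | 1.5 / 15 / 40 |
| Two-sided limit | 0.1 / 0.1 / 0.2 | 0.7 / 3.2 / 6.7 | 0.5 / 8 / 27 |
| Mean of two readings | 0.1 / 0.1 / 0.1 | 0.4 / 2.4 / 5.8 | 0.2 / 5 / 21 |

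The fresh-baseline row isolates the selection effect: an excess of about 0.3, 1.4 and 3 percentage points in responders. At SD 4 that is 0.014 × 15 = 0.2 of a child. The last two rows also remove ordinary measurement noise, so their whole advantage is not bias removal.

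**Proceed.** With no true change, P(≥5 of 15) as written is 0.00%, 0.15% and 2.7%. With a true 5-letter gain and SD 4, the responder probability is about 26.5% as written and 21.3% with a fresh baseline, and Proceed is reached about 36% and 20% of the time.

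**Sensitivity.** A true-acuity SD of 10 changes little. Reading the limit as one logMAR line (5 letters) gives mean gains of 0.5, 1.0 and 1.5 letters. Error SD 2.5 gives 0.4% responders; SD 6 gives 18%, with Proceed at about 12%.

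**Children who fell.** Those who fell 5 or more letters before entry are 17%, 28% and 36% of children enrolled under the current rule. Of them, 5%, 14% and 21% reach +10 with no true change.

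**The case against.** - **Purpose of the rule.** It is meant to exclude children still improving on patching, and limiting improvement does that. This is fair, but the rule also defines stability, and the selection effect follows whatever its purpose.
- **Which reading is the baseline.** The protocol never says outright that the second stability visit is the enrolment reading, and item 5b notes for its own determination that, as a "pre-study procedure, the method of measuring visual acuity is not mandated". If both stability visits came before a separate enrolment test, only the ceiling effect remains, about 0.1 to 0.3 letters. This stands as a real uncertainty. The placing of the stability criterion under the enrolment test favours the other reading, and no later test is required.
- **Noise.** Most no-effect responders come from measurement error at a 10-letter cut without a control, not from the entry rule. This stands.
- **Offsetting features.** Dropouts count as not improved, which pulls the proportion down. Both doses share the rule, so it does not bias the choice between them. Both stand, but neither removes the upward drift among children who are followed.

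A reader might infer that children enrolled on a low reading generally rebound into 10-letter responders, or that rebound alone would carry the pilot to Proceed. The protocol's figures do not support either: at each error SD from 3 to 5 most such children fall short of 10 letters, and Proceed with no effect is at most 2.7%.

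**Conclusion.** The point holds in limited form. The rule is one-sided, the natural reading makes the qualifying acuity the baseline, and no arm cancels the upward drift. The drift is about 0.65 to 1.7 letters in the mean, with a small excess in the responder proportion (0.3 to 3 points over a fresh baseline).

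The practical harm is to the futility decision and to the effect estimate, not a false Proceed from no effect. At SD 4 an ineffective dose escapes Don't Proceed 23% of the time instead of 15%. With a true 5-letter gain, Proceed is reached about 36% of the time instead of 20%.

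These sizes rest on an assumed measurement SD that the protocol does not give, and on the enrolment reading being the second stability reading. They use the cut-offs printed in Table 7-4; section 1.7 names exact intervals, which would move those cut-offs.

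**What to change.** State in 2.2.1 and 2.3.4 which reading is the baseline and whether it is also the second stability reading. Then do one of the following.

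1. **Keep eligibility as it is.** Compute 10-letter improvement from the mean of the two qualifying readings when both are E-ETDRS, and report it beside the current definition. This removes nearly all the mean bias. It costs analysis wording and recording of the earlier reading, which 2.3.1 does not list. The responder rate will look less favourable.
2. **Make stability two-sided in items 3 and 5b.** Require no more than 4 letters of change either way, and allow a later retest for a child who fails only because of a fall. Roughly 17% to 36% of otherwise eligible children would need that retest (28% at SD 4, about 8 of 30). Enrolment would slow, which matters because recruitment potential is an objective and recruitment ends on a fixed date.

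Do not use the better of the two readings as baseline. With no true change it creates a spurious loss of 1.4 to 2.2 letters, larger than the gain it would correct.

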3.1 Treatment

Subjects will be prescribed two hours of daily patching plus be randomized to one of two levodopa doses:

- Oral levodopa 0.51 mg/kg/tid with carbidopa 0.17 mg/kg/tid (3 to 1 formulation)
- Oral levodopa 0.76 mg/kg/tid with carbidopa 0.17 mg/kg/tid (approximately 4.5 to 1 formulation)

All subjects will build up to this daily dose over one week with a rapid taper of medication before a primary outcome visit 8 to 10 weeks after starting levodopa/carbidopa treatment. Subjects will continue with the prescribed 2 hours daily patching between the primary outcome visit #2 and the off-treatment visit #3, 8 to 12 weeks after stopping levodopa/carbidopa treatment.

Notes

1. The study will provide patches.
2. A central pharmacy will compound levodopa-carbidopa capsules based upon body weight and ship the study drug to the subject.
3. During the initiation of levodopa-carbidopa therapy, the drugs will be given once daily for three days, twice daily for three days, and three times daily on day 7 of week 1. The drugs will be administered three times daily up until one week prior to the primary outcome visit 8 to 10 weeks after starting treatment.
4. One week prior to the primary outcome visit, the subject will take the drug twice daily for two days, once daily for two days, and then off for three days.
5. Study medications should be administered with meals. For school-age children the midday dose may be given in school if feasible or by administering the midday dose in mid-afternoon after dismissal from school, with the third dose given after dinner.
6. In addition to the study formulation, additional carbidopa may be prescribed at any time to prevent nausea in consultation with the study chair and neurologist serving as the medical monitor, to be paid for by the study.
7. If a subject is noncompliant with treatment, the parents should be encouraged to persist with their efforts to treat to the best of their ability.
8. Prior to deviating from the treatment protocols or prescribing non-protocol treatment, the situation should be discussed with the Protocol Chair.
9. In the case of pregnancy during this study, the levodopa-carbidopa medicine will be discontinued.

3.2 Compliance

A calendar log will be maintained by all subjects on the daily completion of the prescribed patching treatment and consumption of the oral medication. These logs will be reviewed by the investigator at each of the protocol visits. The investigator's assessment of compliance will be

714 recorded on the Follow-up Examination Form. In addition, compliance will be queried during
715 the phone calls at weeks 1, 2, and 6.

716

717 Medication containers will be brought to the 4-week and primary outcome visits. The amount of
718 remaining medication will be recorded.

719

720 **3.3 Adverse Events**

721 Reporting of adverse events is described in Chapter 6.

722

723 **3.4 Dose Changes**

724 A pediatric neurologist with experience using levodopa-carbidopa in children will serve as
725 consultant expert for the investigators and protocol chairman for review of side-effects and
726 provide consultations for dosage adjustments.

727

728 **3.4.1 Overdosage**

729 Supportive measures along with gastric lavage and monitoring for cardiac arrhythmias are
730 recommended. Pyridoxine has been suggested to reverse the actions of levodopa, but is not
731 considered effective.

732

733 **3.4.2 Discontinuation of Treatment**

734 Blepharospasm or dyskinesia may be an early indication of excess dosage.⁶ The development of
735 these signs should be discussed immediately with the protocol chair and medical monitor to
736 determine if the drug should be discontinued.

737

Chapter 4: Follow Up

